## 5) Analysis by dose of previous ESA formulation types

An analysis similar to “1) Study drug dosage” should be conducted for weekly dose (epoetin alfa, epoetin beta or epoetin kappa:  $\geq 4500$  IU,  $< 4500$  IU; other:  $\geq 15$   $\mu$ g,  $< 15$   $\mu$ g; 2 categories) by type of previous ESA formulation (epoetin alfa, epoetin beta or epoetin kappa, darbepoetin alfa, epoetin beta pegol). Only the MT-6548 group is analyzed.

## 6) Analysis by Hb value on the first day of the treatment period

An analysis similar to “1) Study drug dosage” should be conducted for the Hb value on the first day of the treatment period (subjects are divided into 3 categories with equal population).

## 7) Analysis with or without iron supplements and iron-containing phosphate binders

An analysis similar to “1) Study drug dosage” should be conducted for subjects continuously using iron supplements or iron-containing phosphate binders and subjects never using iron supplements and iron-containing phosphate binders during the treatment period. However, subjects who uses intravenous iron at least once should be excluded from the tabulation. Only the MT-6548 group is analyzed.

Since intravenous iron should be included in the tabulation for treatment period phase 1, the tabulation for treatment period phase 1 should be output again.

## 8) Analysis by iron supplements and iron-containing phosphate binders formulations

An analysis similar to “1) Study drug dosage” should be conducted for subjects using iron supplements or iron-containing phosphate binders continuously during the treatment period. However, subjects who uses intravenous iron at least once should be excluded from the tabulation. Only the MT-6548 group is analyzed.

## 9) Analysis of the mean dose of the study drug at Week 48 and Week 52 of the treatment period and CRP levels on the first day of the treatment period

For MT-6548 group only, a scatter plot chart should be provided after linear regression with the following variables.

x: Logarithmic CRP value on the first day of the treatment period

y: Mean dose of study drug at Week 48 to Week 52 of the treatment period

## (4) Total number of dosage adjustments

The cumulative total number of dose adjustments during the entire treatment period from the first day of the treatment period to Week 52 of the treatment period should be calculated, and the number and proportion of subjects per cumulative number of adjustments and the 95% CI (Clopper-Pearson [Exact] method) of the proportion should be provided.

The number and proportion of subjects and the 95% confidence interval (Clopper-Pearson [Exact] method) should be provided for the proportion of subjects defined below in each period between scheduled study visits and during the entire period from the first day to Week 52 of the treatment period. If a subject is included in more than one definition, the subject should be counted in each definition.

- ✓ No dose adjustment: No change
- ✓ With dose adjustment: dose adjustment (Dose adjustment), dose increase (Increase), drug interruption (Interrupt)

Dose adjustment (Dose adjustment) should include the number of times of increase, decrease, and interruption, and should not count the increase when it is resumed after interruption. Only the MT-6548 group will be tabulated.

(5) Iron supplement dosage

The following should be provided according to the 3 categories of oral iron supplement, intravenous iron supplement, and iron supplement (any route).

Descriptive statistics of the mean dose of iron supplement per month for each treatment group should be calculated for the screening period, and after the first day of the treatment period, in each period between scheduled study visits and during the entire treatment period from the first day to Week 52 of the treatment period.

Descriptive statistics of the change in the mean dose of iron supplement per month from the baseline (mean dose of iron during the screening period) should be calculated, after the first day of the treatment period, in each period between scheduled study visits and during the entire treatment period from the first day to Week 52 of the treatment period. Before and after comparison should be conducted for changes from baseline using the paired t-test. The changes should be compared between groups using the Student-t test. The mean value of the between-group difference (MT-6548 – darbepoetin), its 2-sided 95% CI, and p-value should be provided. The dosage of iron supplement should be calculated using the dose as iron. If no iron supplement is administered, the dose should be tabulated as 0 mg. Subjects who changed the administration route of an iron supplement during the treatment period and subjects who had never received an iron supplement during the treatment period should be excluded from the tabulation.

(6) Proportion of subjects receiving oral, intravenous, or iron supplement (any route)

The number, proportion, and 95% CI (Clopper-Pearson [Exact] method) of the proportion of subjects treated with oral, intravenous, or oral iron supplement (any route) should be provided by treatment group for the screening period, and after the first day of the treatment period, in each period between scheduled study visits and during the entire treatment period from the first day to

Week 52 of the treatment period. A McNemar tests should be used for before and after comparison between baseline (ratio of subjects receiving iron supplements by the aforementioned route in the screening period) and each period between scheduled study visits. The estimate, its 95% CI (exact method), and p-value (Fisher's exact test) for between-group difference (MT-6548 – darbepoetin) should be calculated for the proportion of subjects receiving oral, intravenous, or (any route) iron supplement.

Subjects who have not received an iron supplement are to be subjects who have never received an iron supplement during the relevant period, and subjects who have received an oral, intravenous, or (any route) iron supplement are to be subjects who have received an iron supplement at least once during the relevant period.

(7) Proportion of subjects with serum ferritin  $\geq 100$  ng/mL or TSAT  $\geq 20\%$ .

The number, proportion, and 95% CI (Clopper-Pearson [exact] method) of the proportion of subjects with serum ferritin levels of  $\geq 100$  ng/mL or TSAT levels of  $\geq 20\%$  should be provided at each evaluation time point of the treatment period for each treatment group. A McNemar tests should be used for before and after comparison between baseline (ratio of subjects receiving iron supplements by the aforementioned route in the screening period) and each period between scheduled study visits. The estimate, its 95% CI (exact method), and p-value (Fisher's exact test) for between-group difference (MT-6548 – darbepoetin) should be calculated for the proportion of subjects with serum ferritin  $\geq 100$  ng/mL or TSAT  $\geq 20\%$ .

(8) Changes and rate of changes in iron-related indices (serum iron, TIBC, TSAT, and serum ferritin levels) and hepcidin from the first day of the treatment period

Iron-related indices (serum iron, TIBC, TSAT, and serum ferritin) and hepcidin should be measured at each evaluation time point of the treatment period, and their changes and rate of changes should be calculated from the first day of the treatment period to each evaluation time point of the treatment period. Descriptive statistics of the measurements, changes, and rate of changes should be calculated for each treatment group. A paired t-test should be performed for before and after comparison of changes and change rates from the first day of the treatment period.

A group comparison should be conducted for the change in iron-related indices (serum iron, TIBC, TSAT, and serum ferritin) and hepcidin from the first day of the treatment period to each evaluation time point using the MMRM model (with compound symmetry [CS] for within-subject variance-covariance matrix). LSMean, its standard errors, and 2-sided 95% CI should be calculated, and the point estimate, its standard errors, 2-sided 95% CI, and p-value should be provided for the group difference (MT-6548 – darbepoetin) of the LSMean by treatment group. Only the serum ferritin value at each evaluation time point of the treatment period should be similarly compared between groups.

The time course diagram of changes in the iron-related indices (serum iron, TIBC, TSAT, and serum ferritin levels) and hepcidin from the first day of the treatment period to each evaluation time point should be prepared for each treatment group. The 95% CI of LSMean will be represented by an error bar. For only the ferritin value, a similar time course diagram should be prepared for ferritin values at each evaluation time point of the treatment period.

The serum ferritin values should be shown as follows.

- ✓ An analysis similar to the above ferritin should be conducted by baseline value (subjects are divided into 3 categories with equal population). The time course diagram of LSMean should be prepared separately by treatment group.
- ✓ The following scatter plot chart should be provided by treatment group. Linear regression should be performed to calculate the p-value and correlation coefficient of the test with zero slope as the null hypothesis.

x: Serum ferritin at baseline

y: Serum ferritin at Week 52 of the treatment period

(9) Changes in hematocrit, red blood cell count, reticulocyte (count and rate), mean corpuscular volume, mean corpuscular hemoglobin, and EPO from the first day of the treatment period

Descriptive statistics of hematocrit, red blood cell count, reticulocyte (count and rate), mean corpuscular volume, mean corpuscular hemoglobin, and EPO at each evaluation time point should be calculated for each treatment group. The change from the first day of the treatment period should be obtained, and the descriptive statistics should be calculated for each treatment group.

A group comparison should be conducted for the change in hematocrit, red blood cell count, reticulocyte (count and rate), mean corpuscular volume, mean corpuscular hemoglobin, and EPO from the first day of the treatment period to each evaluation time point. MMRM (with compound symmetry [CS] for within-subject variance-covariance matrix) is used to calculate LSMean and its standard error and 2-sided 95% CI for each treatment group, and the point estimate, its standard error, the 2-sided 95% CI, and p-value of the between-group difference (MT-6548 – darbepoetin groups) of LSMean are shown.

For hematocrit, red blood cell count, and reticulocyte (count and rate), neither comparison of before and after changes in the darbepoetin group nor comparison with the darbepoetin group was performed.

A histogram of EPO measurements should be prepared for evaluation time point at Week 52 of the treatment period.

(10) Changes in systolic blood pressure, diastolic blood pressure, and blood glucose from the first day of the treatment period, changes and rate of changes in lipid (total cholesterol, LDL-C, HDL-C, LDL-C/HDL-C ratio, triglycerides) from the first day of the treatment period

Confidential

Systolic blood pressure, diastolic blood pressure, lipids (total cholesterol, LDL-C, HDL-C, LDL-C/HDL-C ratio, triglycerides), and blood glucose should be analyzed in the same manner as hematocrit, red blood cell count, and reticulocyte (count and rate) in the preceding section.

Descriptive statistics for each measurement at the evaluation time point of Week 52 of the treatment period should be calculated for each treatment group by baseline value (subjects are divided into 3 categories with equal population). The change from the first day of the treatment period should be obtained, and the descriptive statistics should be calculated for each treatment group. A paired t-test should be performed for before and after comparison of changes from the first day of the treatment period. A group comparison should be conducted for the change from the first day of the treatment period using the MMRM model (with compound symmetry [CS] for within-subject variance-covariance matrix). The LSMean for each treatment group is calculated, and the point estimate of the between-group difference (MT-6548 – darbepoetin) of LSMean, its standard error, 2-sided 95% CI, and p-value were shown.

Descriptive statistics should be similarly calculated for each treatment group on the rate of change from the first day of the treatment period at each evaluation time point of the lipid (total cholesterol, LDL-C, HDL-C, LDL-C/HDL-C ratio, triglycerides), and a group comparison should be conducted using the MMRM model (with compound symmetry [CS] for within-subject variance-covariance matrix).

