13.1 Analysis sets

Efficacy analysis is performed with the full analysis set (FAS). Primary endpoint analysis will also be performed with the set of subjects conforming to the protocol, or the per-protocol set (PPS). Safety analysis will be performed with the safety analysis set.

Analysis sets are defined below; details of subject handling for Phase 1 data and final data will be determined by the study sponsor before each dataset is locked.

(1) Efficacy analysis set

1) FAS

The FAS consists of all randomly allocated subjects excluding the following subjects:

- ✓ Subjects who did not have HD-CKD-related anaemia
- ✓ Subjects who did not use a single dose of study drug
- ✓ Subjects with absolutely no post-randomization efficacy data

2) PPS

The PPS consists of the FAS with the following subjects excluded:

- ✓ Subjects with deviations from inclusion criteria
- ✓ Subjects who met exclusion criteria

- ✓ Subjects who violated rules concerning prohibited concomitant drugs or therapies
- ✓ Subjects with <80% compliance rate for either MT-6548 Tablet 150 mg or darbepoetin alfa injection active comparator

(2) Safety analysis set

The safety analysis set consists of all randomly allocated subjects excluding the following subjects:

- ✓ Subjects who did not use a single dose of study drug
- ✓ Subjects with absolutely no post-randomization safety data

(3) Drug concentration analysis set

The drug concentration analysis set consists of all randomly allocated subjects excluding the following subjects:

- ✓ Subjects who did not use a single dose of MT-6548 Tablet 150 mg
- ✓ Subjects with absolutely no post-randomization plasma drug concentration data

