13.3.2 Efficacy

(1) Analysis methods for primary endpoint

For the primary endpoint of mean Hb at treatment period Weeks 20 and 24, mean Hb at each timepoint will be modeled using MMRM with the following model, mean Hb at treatment period Weeks 20 and 24 will be calculated for each group, and point estimates and their two-sided 95% CI will be calculated for differences in mean values between the MT-6548 group and the darbepoetin group. Non-inferiority of MT-6548 to darbepoetin alfa (recombinant) will have been established if the lower limit of the 95% CI is ≥ -0.75 g/dL.

[MMRM model]

- Covariates: Baseline values
- Fixed effects: Treatment group, evaluation period, interactions of evaluation period \times treatment group, Random effects: Subjects
-

The non-inferiority of the MT-6548 group with the darbepoetin group will be assessed after the mean of mean Hb values at treatment period Weeks 20 and 24 and its 95% CI is confirmed to fall within the target range of Hb values (10.0–12.0 g/dL).

Sensitivity analysis will be performed using the following analysis methods.

- 1) Tipping point analysis
- 2) ANCOVA using data with missing values imputed by LOCF and baseline values as covariates

(2) Analysis methods for secondary endpoints

1) Mean Hb at treatment period Weeks 48 and 52

Treatment groups will be compared using the same analysis methods (MMRM) used for the primary endpoint. Point estimates and their standard errors and 95% CI will be calculated for differences in mean values between the MT-6548 group and the darbepoetin group.

2) Hb at each treatment period timepoint

Descriptive statistics will be calculated for Hb levels at each treatment period timepoint, and analysis performed taking into account changes over time using MMRM.

3) Proportion of subjects with mean Hb levels within the target range (10.0–12.0 g/dL), <10.0 g/dL, and ≥ 12.0 g/dL at each timepoint in the treatment period

Numbers and ratios of subjects with mean Hb at each treatment period timepoint within

the target range (10.0–12.0 g/dL), <10.0 g/dL, and ≥ 12.0 g/dL will be shown.

(3) Other endpoints

Incidence and ratios will be shown for discrete data, while descriptive statistics will be calculated by treatment group for continuous data.

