## 8.5 Efficacy analysis

As a general rule, efficacy analysis will be performed on the FAS. When necessary, descriptive statistics for continuous variables should be calculated and frequency and proportion will be calculated for discrete variables. No data from the day after the rescue therapy implementation date should be included in the efficacy analysis.

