## 10. Changes in the Statistical Analysis Plan from the Study Protocol

No change from the study protocol.

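### The between-arm test of monthly iron dose excludes subjects with no iron or a route change on treatment, and neither SAP's methods text describes a dose comparison in the whole FAS

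*SAP*

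**What the plan says.** Final SAP 8.5.2 (5) tabulates the mean monthly iron dose for oral, intravenous and any-route iron, and its change from the screening period, for each visit interval and for the whole treatment period. For the arms it states: "The changes should be compared between groups using the Student-t test", with the mean difference, 95% CI and p-value. On non-use it states: "If no iron supplement is administered, the dose should be tabulated as 0 mg". The next sentence removes two groups. The first is the route changers: "Subjects who changed the administration route of an iron supplement during the treatment period". The second is those with no iron on treatment, by this wording: "subjects who had never received an iron supplement during the treatment period should be excluded from the tabulation". Phase 1 SAP 8.5.3 (5) and Final SAP 8.7.1 carry the same rule.

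Final SAP 8.5 sets the population: "As a general rule, efficacy analysis will be performed on the FAS". Protocol 13.1 also names the FAS for efficacy. Protocol 8.5.2 (1) leaves iron dose and route to the investigator, subject to the ferritin/TSAT maintenance rule. For the other endpoints, protocol 13.3.2 (3) plans only this: "while descriptive statistics will be calculated by treatment group for continuous data". Final SAP section 10 reads: "No change from the study protocol".

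**The concern.** Whether a subject takes any iron on treatment, and whether the route changes, is settled after randomisation by investigators responding to iron indices. Treatment can affect both, so the retained subjects need not be comparable between arms. The never-iron rule does two different things. Dropping screening non-users who never start (change 0) only alters the denominator. Dropping screening users who take no iron at all on treatment removes the largest possible decreases, although the 0 mg rule gives them a value. Route changers are dropped even from the any-route table, with no reason given.

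The treatment period is defined as running to its final day, so an early-visit test also selects on later iron use. At stake is a difference, CI and p-value that could be taken for the effect of randomised treatment on iron dose.

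**Working it through.** The plan states no user rate, dose, SD or power for iron dose, so there is no figure to reproduce and every input below is an assumption. The unit is percent of a screening user's dose, and differences are MT-6548 minus darbepoetin. The central case has 50% on iron at screening; brackets give 30% and 70%.

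**Identity.** For each arm let s be the share on iron at screening, q the share of those with no iron at all on treatment, and R the share retained by the never-iron rule. A dropped non-user contributes 0 and a dropped screening user contributes -100. With no route change:

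planned mean = (all-FAS mean + 100 × s × q) / R

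If q = 0 in both arms and R is equal, the planned difference is the all-FAS difference divided by R, which is pure rescaling.

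**A. Time-based model.** Twelve monthly steps; start or restart risk 2%; stop risk 3% (darbepoetin) against 6% (MT-6548).
- q = stop risk × 0.98^11: 0.024 and 0.048. Non-users who never start: 0.98^12 = 0.785.
- R = 0.5 × (1 - q) + 0.5 × (1 - 0.785): 0.596 and 0.584.
- All-FAS means from the chain: -2.72 and -9.85, difference **-7.1** (-4.7, -9.6).
- Planned: (-2.72 + 1.20)/0.596 = -2.55 and (-9.85 + 2.40)/0.584 = -12.76, difference **-10.2** (-9.0, -11.0).
- With 15% or 30% monthly stopping on MT-6548: -21.6 against -30.9, and -33.4 against -46.8. The sign is the same.

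**B. First month of A, same exclusions.**
- All-FAS: 0.5 × (-3) + 0.5 × 2 = -0.5 and 0.5 × (-6) + 0.5 × 2 = -2.0, difference **-1.5** (-0.9, -2.1).
- Planned: (-0.5 + 1.20)/0.596 = 1.17 and (-2.0 + 2.40)/0.584 = 0.68, difference **-0.5** (-0.4, -0.6).
- The early-visit difference shrinks while the whole-period difference grows.

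**C. What a sign change needs in A.** Add MT-6548 screening users who take no iron on treatment until the planned difference is 0.
- 3% against 6% monthly stopping: 56% (43%, 71%) of MT-6548 screening users have no iron on treatment, against 2% of darbepoetin screening users. The all-FAS difference there is -25.9.
- 3% against 4%: 30% (21%, 46%). The all-FAS difference there is -13.6.

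**D. Treatment acts only through complete stopping.** q is 15% on MT-6548 and 10% on darbepoetin; n is the share of non-users who start iron.
- All-FAS mean = 100 × [(1 - s)n - s × q]. With n = 0.2: 2.5 and 5.0, difference **-2.5** (-1.5, -3.5).
- Planned mean = 100 × (1 - s)n / [s(1 - q) + (1 - s)n]: 10/0.525 = 19.05 and 10/0.55 = 18.18, difference **+0.9** (+1.3, +0.5).
- With n = 0 both planned means are 0 and the planned difference is exactly 0.
- A simulation with 150 per arm, 40% against 20% complete stopping, 15% of non-users starting and user dose mean 100, SD 50 mg/month gave -10.1 all-FAS and +4.4 planned, with rejection in 26% and 6% of trials. With 20% stopping in both arms, both differences were near 0 with about 5% rejection.

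**E. Same use in both arms, 20% lower dose among MT-6548 users.** With q = 0.1 and n = 0.2, R = 0.55. All-FAS is -11.0 and planned is -11.0/0.55 = -20.0: rescaling only.

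**F. Route change in 20% (MT-6548) against 10% of screening users.**
- All-FAS = 100 × 0.5 × 0.10 × (d - 1), where d is the changers' dose ratio: -2.5 (-1.5, -3.5) if their dose halves, +5.0 (+3.0, +7.0) if it doubles.
- Planned is 0.0 in both cases if no non-user starts, and +1.8 (+2.7, +1.0) in both if 20% start. Changers' doses never enter.

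**The case against.** The best defence is that items (5) and (6) form a pair. Item (6) counts non-users and gives McNemar tests against screening and a between-arm difference with CI and Fisher p-value, so excess complete stopping would show there. Items (7) and (8) carry no such exclusion. The FAS sentence is a general rule that admits exceptions, and this exclusion is stated openly. Phase 1 SAP 8.5.4.7 calls these endpoints exploratory. Inferential tests beyond the protocol's descriptive plan run throughout the SAP's other endpoints, so the section 10 discrepancy is not peculiar to this item.

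Most of this stands and limits the weight of the point. It does not repair the test: item (6) compares proportions, items (7) and (8) compare iron indices, and none compares dose between the randomised groups. Route changers' doses are not compared between arms anywhere in the methods text.

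A reader might infer that the exclusion generally reverses the difference. Scenarios A and E do not support that: the usual effect is rescaling with the same sign. Nor is the sign wrong whenever treatment acts only through stopping; that also requires some screening non-users to start iron. A reader might also infer that no all-FAS table exists. The output table lists are not in the text available for this review, so only the methods text can be said to describe none.

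**Conclusion.** The point holds and should be fixed, within limits. A t-test, CI and p-value are attached to a group selected by two post-randomisation conditions, when the SAP's own 0 mg rule allows the never-iron subjects to be kept. The actual size cannot be computed, because the documents give no iron-use, stopping or route-change rates.

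On the assumed inputs the whole-period result is mostly moved to a per-user scale, and an early-visit result can shrink to about a third. Loss or reversal of the difference needs one of three things: treatment acting only through complete stopping, a large between-arm gap in complete stopping (scenario C), or an effect that runs through route changers. The endpoint is exploratory. Nothing here bears on the primary Hb analysis or the non-inferiority conclusion.

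**What to change.** In Final SAP 8.5.2 (5), replace the exclusion sentence with: *The between-group comparison includes all FAS subjects with a calculable dose. On-study time without iron by the relevant route counts as 0 mg. Subjects who changed route are kept. Each subject's time ends on the day before discontinuation (4.13), and data from the day after rescue therapy stay excluded (8.5). The number of subjects whose dose cannot be calculated because of as-needed iron is given by treatment group.*

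Then:
- Keep the existing table as descriptive, labelled *on-treatment iron users without route change*, without a between-arm p-value, to be read with item (6).
- Keep 8.7.1 on the Phase 1 method and add one all-FAS Week 24 table, labelled as a post-lock addition under protocol 13.4.
- State the test, its population and the reason in section 10.

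The cost is one changed filter, one count by arm, one added table, a label and a section 10 entry. No new data are needed.

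The downsides should be stated:
- The all-FAS difference is per randomised subject, so it is usually smaller than a per-user figure.
- The change comes after the Phase 1 analysis, and the Week 52 test would not be directly comparable with the Phase 1 test; the added Week 24 table addresses this.
- The any-route dose sums oral and intravenous milligrams, so a switch alone can move it; the separate oral and intravenous tables show this.
- Later-visit comparisons still lose subjects who discontinued.
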